9.5. Pregnancies

For any subjects in the Treated population who become pregnant during the study, every attempt will be made to follow these subjects to completion of pregnancy to document the outcome, including information regarding any complications with pregnancy and/or delivery. Note that the CSR will not be delayed to wait for outcomes of any pregnancies; an addendum to the CSR would be provided in such a scenario. A set of listings of pregnancies and outcomes will be presented (Listing 18, Listing 19, Listing 20, Listing 21, and Listing 22).

9.6. Clinical Laboratory Evaluations

Clinical safety laboratory adverse events are collected Day 1, 3, 5, 8, 11 and Day 15 and 29 if able to return to clinic or still hospitalized. Parameters evaluated include white blood cell count, absolute neutrophil count, eGFR, platelet count, hemoglobin concentration, creatinine, glucose, total bilirubin, ALT, AST, INR, d-dimer, and CRP. Laboratory safety parameters will be graded according to the Division of AIDS (DAIDS) Table for Grading the Severity of Adult and Pediatric Adverse Events, version 2.1 (July 2017). For sites that do not

report an upper (lower) limit for the value of a laboratory parameter, the median of the reported upper (lower) limits across the other sites will be used. Medians and calculated LLN/ULN used if any, will be documented in the ADaM documentation. Vitamin D is collected on Day 1 and is not graded, but results will be summarized.

The distribution of Grade 3 and 4 chemistry and hematology laboratory results by maximum severity, time point, actual baseline ordinal score and treatment group will be presented ([Table 88](#)). Treatment-emergent laboratory abnormalities will be summarized by parameter and grade ([Table 89](#)).

Descriptive statistics including mean, median, standard deviation, maximum, and minimum values and change from baseline by time point, for all and each chemistry and hematology laboratory parameter will be summarized by actual baseline ordinal score and treatment arm ([Table 51](#) and [Table 90](#)). Changes in chemistry and hematology laboratory values will be presented in line graphs over time with median, Q1 and Q3 plotted by actual baseline ordinal score and treatment arm ([Figure 34](#)).

Listings will provide a complete listing of individual chemistry and hematology laboratory results with applicable reference ranges ([Listing 23](#)).

9.7. Vital Signs and Physical Evaluations

Vital sign measurements include pulse, systolic blood pressure, respiratory rate, SpO₂ and oral temperature. Vital signs were assessed as part of the NEW score (assessed at Day 1) and will be listed in [Listing 24](#).

Targeted Physical examinations are performed at Day 1 and may be performed post-baseline only when needed to evaluate possible adverse events. At the screening visit, the targeted physical examination is focused on lung auscultation. Physical exam findings per subject will be detailed in a listing ([Listing 25](#)).

9.8. Concomitant Medications

Concomitant medications will be coded to the Anatomical Therapeutic Classification using the WHO Drug Dictionary. The use of prior and concomitant medications taken during the study will be recorded on the CRFs. Concomitant medication and corticosteroid use will be presented in subject listings ([Listing 9](#) and [Listing 10](#)). The use of concomitant medications during the study (regardless of whether the medications were started prior to enrollment or after enrollment) will be summarized by ATC1, ATC2 code, actual baseline ordinal score and treatment group for the As Treated population ([Table 55](#)).

9.9. Other Safety Measures

No additional safety analyses are planned.

10. PHARMACOKINETICS

Not applicable.

11. IMMUNOGENICITY

Not applicable.

12. OTHER ANALYSES

Not applicable.

13. REPORTING CONVENTIONS

P-values ≥ 0.001 and ≤ 0.999 will be reported to 3 decimal places; p-values less than 0.0005 will be reported as “ <0.001 ” and p-values greater than 0.9995 will be reported as “ >0.999 ”.

The mean, confidence intervals, median, IQR, and other statistics will be reported to 1 decimal place greater than the original data. The minimum and maximum will use the same number of decimal places as the original data.

Proportions will be presented as 2 decimal places; values greater than zero but <0.005 will be presented as “ <0.01 ”. Percentages will be reported to the nearest whole number; values greater than zero but $< 0.5\%$ will be presented as “ <1 ”; values greater than 99.5% but less than 100% will be reported as “ >99 ”.

For all other estimators, the NEJM statistical reporting guidelines will be followed: results will be presented with no more precision than is of scientific value and is meaningful. For example, measures of association, such as odds ratios, will be reported to two or three significant digits. Results derived from models will be limited to the appropriate number of significant digits.

14. TECHNICAL DETAILS

SAS version 9.4 or above, or R language and environment for statistical computing 3.6.1 or above, will be used to generate all tables, figures and listings.

15. SUMMARY OF CHANGES IN THE CONDUCT OF THE STUDY OR PLANNED ANALYSES

15.1. Test Statistic for Primary Endpoint of Time to Mechanical Ventilation or ECMO

The test statistic in Section 8.1.1 was modified to account for unequal weighting in each stratum. The weighting is based on the inverse variance of the difference of the complementary log-log transformation of the Kaplan-Meier estimator at Day 29. The version of the formula reported in Klein 2007 gave equal weight to each stratum. As rationale for the modification, consider the extreme scenario where the difference in Kaplan-Meier Estimators is 10% in one stratum and -10% in the other stratum. However, the first stratum has n=10,000 and the second stratum has n=100. Using the original formula, both strata would be equally weighted and show no difference. By adding a weighting to the formula, the strata with the higher information will be given more weight in computing the final test statistic.

15.2. AE Reporting of Clinical Laboratory Results for eGFR, Creatinine, INR and Glucose

The DAIDS Toxicity Table will be applied to clinical laboratory results and the corresponding grade 3 or 4 AEs reported based on these laboratory results, with the below clarifications for AE reporting.

15.2.1. eGFR and Creatinine Grading

The DAIDS Toxicity Table has two grading options for eGFR and Creatinine, “Change from baseline” or “absolute value”. The absolute values will be used for AE reporting.

15.2.2. Glucose Grading

No change to the grading per the DAIDS Toxicity Table. However, a baseline condition of diabetes mellitus will be factored into reporting of grade 3 or grade 4 adverse events, as follows:

- If a subject has no history of any type of diabetes mellitus and baseline glucose levels are normal, grade 1 or grade 2, then any grade 3 or 4 glucose spike will be reported as an AE.
- If a subject has a history of any type of diabetes mellitus, then:
 - All grade 4 glucose elevations will be reported as AEs.
 - If baseline glucose levels are normal, grade 1, grade 2 and there are two or more consecutive elevations of glucose to grade 3, this will be reported as an AE.
 - If baseline glucose levels are normal, grade 1 or grade 2, a single elevation of glucose to grade 3 will not be reported as an AE or reported as related to Dexamethasone.

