3. STUDY OBJECTIVES AND ENDPOINTS

3.1. Study Objectives

Primary Objective

To evaluate the clinical efficacy of baricitinib + remdesivir versus dexamethasone + remdesivir as assessed by the **mechanical ventilation free survival** by Day 29.

Secondary Objectives

The key secondary objective is to evaluate the clinical efficacy of baricitinib + placebo + remdesivir versus placebo + dexamethasone + remdesivir according to the clinical status 8-point ordinal scale at Day 15.

The other secondary objectives are to evaluate clinical efficacy of baricitinib + placebo + remdesivir as compared placebo + dexamethasone + remdesivir as assessed by:

- Among subjects with actual baseline Clinical Status ordinal score in Ordinal Score 5, the proportion that do not progress to Clinical Status score 6, 7, or 8 at any time prior to Day 29.
- Mortality
 - Death by Day 15
 - Death by Day 29
- Time to recovery by Day 29.
- Time to an improvement of one category and two categories from Day 1 using the ordinal scale.
- Subject clinical status using 8-point ordinal scale at Days 3, 5, 8, 11, 15, 22, and 29.
- Desirability of Outcome Ranking (DOOR) at Day 15 and Day 29.
- Oxygenation:
 - Oxygenation use up to Day 29.
 - Incidence and duration of new oxygen use through Day 29.
- Non-invasive ventilation/high flow oxygen:
 - Non-invasive ventilation/high flow oxygen use up to Day 29.
 - Incidence and duration of new non-invasive ventilation or high flow oxygen use through Day 29.
- Invasive Mechanical Ventilation / extracorporeal membrane oxygenation (ECMO):
 - Ventilator/ECMO use up to Day 29.
 - Incidence and duration of new mechanical ventilation or ECMO use through Day 29.
- Duration of hospitalization (in days) through Day 29.
- Laboratory Efficacy assessed by d-dimer, and C-reactive protein (CRP) over time

Safety Objectives

Evaluate the safety of baricitinib + remdesivir and dexamethasone + remdesivir through 29 days of follow-up as assessed overall by:

- Cumulative incidence of SAEs through Day 29
- Cumulative incidence of Grade 3 and 4 clinical and/or laboratory AEs through Day 29.
- Discontinuation or temporary suspension of study product administrations (for any reason).
- Changes in white cell count (WBC) with differential, hemoglobin, platelets, creatinine, glucose, total bilirubin, alanine aminotransferase (ALT), aspartate aminotransferase (AST), prothrombin time (PT reported as and INR) over time (analysis of lab values in addition to AEs noted above).

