Desirability of outcomes response (DOOR) is an ordinal scale combining current clinical status with SAEs. SAE may be related or unrelated to study product. Any SAE occurring after study product administration through Day 15 (or through Day 29) will be counted:

- 1- Recovered (Ordinal Score Category 1,2,3)
- 2- Improved by at least 1 Ordinal Score from baseline & no SAE
- 3- Improved by at least 1 Ordinal Score Category from baseline & SAE
- 4- No change in Ordinal Score Category from baseline & no SAE
- 5- No change in Ordinal Score Category from baseline & SAE
- 6- Worsened by at least 1 Ordinal Score Category from baseline
- 7- Death (Ordinal Score Category 8)

Oxygenation, Non-invasive ventilation/high flow oxygen, Invasive Mechanical Ventilation/extracorporeal membrane oxygenation (ECMO), hospitalization and mortality will be assessed using results of the Clinical Status 8-point ordinal scale, medical history, and post discharge eCRF questions.

Safety will be assessed by the following:

- Cumulative incidence of serious adverse events (SAEs) through 28 days of follow-up.
- Cumulative incidence of Grade 3 and 4 treatment-emergent AEs.
- Discontinuation or temporary suspension of study product administration (for any reason).
- Changes in white cell count, hemoglobin, platelets, creatinine, total bilirubin, ALT, AST, and INR, d-dimer, C-reactive protein over time. Note D-dimer and CRP are not graded.
- Time to the Composite Endpoint of the first of death, SAE, or Severe AE from the day of first dose of study treatment to the earliest date of any of these events.

Clinical labs will be drawn on Days 1, 3, 5, 8, 11 and on Day 15 and 29 if the subject is able to return to the clinic or is still hospitalized. CRP values from sites using a high-sensitivity assay will be excluded from all CRP summaries and any analyses that use CRP values.

Virologic efficacy is an exploratory endpoint and will be assessed by the following:

- Qualitative and quantitative PCR for SARS-CoV-2 in OP swab on Days 1, 3, 5, 8, 11 (while hospitalized); and Day 15 and 29 (if able to return to clinic or still hospitalized).
- Qualitative and quantitative PCR for SARS-CoV-2 in blood on Days 1, 3, 5, 8, 11 (while hospitalized).

The schedule of study procedures is provided in Section 1.2 of Appendix D of the study protocol.

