9.3. Adverse Events

For the calculation of incidence of adverse events (i.e., on a per subject basis), each subject will only be counted once and any repetitions of adverse events within a subject will be ignored; the denominator will be the number of subjects in the As Treated population. All adverse events reported and treatment emergent will be reported in tables and listings; treatment emergent events are adverse events or events increasing in severity anytime following the initiation of administration with any study product (baricitinib, dexamethasone, remdesivir, or any placebo).

An overall summary by treatment arm and actual baseline ordinal score of adverse events is presented that includes, but not limited to: subjects with at least one event, at least one related event, at least one SAE, at least one related SAE and at least one AE leading to early termination for all subjects ([Table 60](#) and [Table 61](#)).

Adverse events occurring in 5% of subjects (by MedDRA preferred term) in any treatment group will be presented ([Table 63](#)).

The proportion of subjects reporting at least one adverse event will be summarized by MedDRA system organ class and preferred term for each treatment arm, actual baseline ordinal score and overall. Denominators for percentages are the number of subjects in the Treated population.

The following summaries for adverse events will be presented by MedDRA system organ class, preferred term, baseline ordinal score and treatment group:

- Renal adverse events by preferred term ([Table 64](#));
- Hepatic adverse events by preferred term ([Table 65](#))
- Related adverse events by MedDRA system organ class and preferred term ([Table 66](#));
- Subject listing of non-serious adverse events ([Listing 13](#)) and listing of related adverse events ([Listing 14](#));
- Bar chart of non-serious related adverse events by actual baseline ordinal score and MedDRA system organ class ([Figure 25](#), [Figure 26](#));

A table of new diagnoses between the Day 29 visit and the Day 60 visit will be summarized by condition, treatment arm, actual baseline ordinal score and overall ([Table 67](#)). Conditions reported at the Day 60 visit will be listed ([Listing 30](#)).

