15.3. Changes to the SAP from Version 1.0 to Version 2.0

The below summarizes the changes made to the SAP from version 1.0 to version 2.0.

- As described in Section 15.1, the primary analysis was updated to use a weighted test statistic.
- As described in Section 15.2, text was added to describe reporting of AEs for eGFR, Creatinine, Glucose and INR.
- It was decided that the Day 60 analyses would be included in the final study report, rather than an addendum. The SAP was amended to include data through Day 60.
- At the time of the SAP update, all subjects were enrolled and there was only one known stratification error where a subject was neither ordinal score 5 nor 6 at baseline. Since only one subject fell into the “other” category in SAP version 1.0, tables were updated to include the one stratification error in the overall summaries but exclude the subject from subgroup analyses and modeling with adjustments for baseline strata. The SAP was left flexible enough to handle any additional stratifications errors identified prior to database lock.
- Modeling including baseline strata was updated to only be run based on handling the baseline ordinal score as continuous since there are only two levels included (i.e., baseline ordinal score 5 or 6).
- SAP version 1.0 table title “Infections by Treatment Group” was updated to be “Culture Results by Treatment Group and AE Severity”. Additional tables of infections by MedDRA preferred term were added.
- Section 3.3.3, the following sentence was removed: “Subjects who are randomized but do not initiate treatment will be censored at time 0.” Additionally, the following sentence was added: “Subjects not completing Day 29 or discharged to hospice or other end-of-life care prior to Day 29 with a death date unknown but completing Day 60 will be reviewed by the blinded Endpoint Review Committee to assess whether the Day 60 data impacts handling of the subject for the Day 29 timepoint.”
- Throughout the document:
 - Typos and errors introduced via copying/pasting language from other sections were corrected.
 - Clinical Status was updated to be “Ordinal Score” in the tables for consistency with language used in prior ACTT clinical study reports.
 - Titles for tables and figures were updated to include “by Day 29”, where applicable, to distinguish from Day 60 outcomes.

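### The glucose reporting rule in SAP Section 15.2.2 may remove more grade 3 events from the dexamethasone arm than from the baricitinib arm, and no safety comparison without the rule is planned

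*SAP*

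**What the plan says.** The safety objectives in SAP Section 3.1 include "Cumulative incidence of Grade 3 and 4 clinical and/or laboratory AEs through Day 29". Section 3.2 lists grade 3 and 4 treatment-emergent AEs as a safety endpoint. Section 3.3.14 makes them the third component of the composite with death and SAE.

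Section 15.2.2 leaves the DAIDS grading of glucose unchanged but makes AE reporting depend on diabetes history:

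- No history of diabetes, baseline normal to grade 2: "then any grade 3 or 4 glucose spike will be reported as an AE".
- History of diabetes, any baseline: "All grade 4 glucose elevations will be reported as AEs".
- History of diabetes, baseline normal to grade 2, repeated values: if "there are two or more consecutive elevations of glucose to grade 3, this will be reported as an AE".
- History of diabetes, baseline normal to grade 2, one value: "a single elevation of glucose to grade 3 will not be reported as an AE or reported as related to Dexamethasone".

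Section 15.3 lists this text among the changes made in version 2.0. It also says "At the time of the SAP update, all subjects were enrolled" and speaks of database lock as still to come. Section 15.1 explains why the test statistic was changed, but Section 15.2.2 gives no reason for the glucose rule. Section 9.9 plans no further safety analyses.

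**The concern.** The trial compares two anti-inflammatory drugs head to head, and severe AEs are one of its main safety contrasts. Under Section 15.2.2, a glucose value that is still graded severe is left out of the AE count because of the subject's history. The only drug the rule names is the randomized component of one arm.

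If dexamethasone raises the risk of an isolated grade 3 value in diabetics, the rule takes more events from the dexamethasone arm than from the baricitinib arm. The grade 3/4 AE difference in Table 61, the rates in Table 76 and the hazard ratio in Table 77 would then understate dexamethasone's contribution. A reader of those tables could not tell, because no version without the rule is planned.

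**Working it through.** **What the rule reaches.** An event not reported as an AE cannot enter the grade 3-4 row of Table 61, Table 76, or the third component of the Table 77 composite. Table 88 (grade 3/4 results), Table 89 (treatment-emergent abnormalities by grade) and Table 90 (summary statistics) are built from laboratory values, so they are unaffected. They do not feed the three AE tables.

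**The same value in two subjects.** Each has normal baseline glucose and one grade 3 value. The subject without diabetes has a grade 3 AE. The subject with diabetes has none, and enters the composite only through some other event.

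**Size.** The SAP states no glucose event rate and no share of diabetics, so there is no figure to reproduce. The inputs below are assumptions, apart from the planned total.

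- N = 750 per arm: the planned total of about 1500 in Section 5, divided by 2, assuming equal allocation.
- d = share of subjects with diabetes history and baseline glucose normal to grade 2: 35% to 40%. Diabetics with worse baseline glucose would lower it.
- g = risk of an isolated grade 3 value among them: 10% to 15% on dexamethasone, 3% to 5% on baricitinib.
- b = share already counted through another grade 3/4 AE: 30% in both arms, taken as independent.

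Share removed per arm = d × g × (1 − b). Arm difference removed = d × (g_dex − g_bari) × (1 − b).

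- No excess (g equal in the two arms): difference removed = 0, with a 50:50 split of removed subjects.
- Smallest excess within these ranges: 0.35 × (0.10 − 0.05) × 0.70 = 0.01225, or 1.2 points. Subjects removed: 750 × 0.35 × 0.10 × 0.70 = 18.4 against 9.2.
- Largest excess within these ranges: 0.40 × (0.15 − 0.03) × 0.70 = 0.0336, or 3.4 points. Subjects removed: 750 × 0.40 × 0.15 × 0.70 = 31.5 against 6.3.

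For scale, take a 30% event rate in each arm. The standard error of the arm difference is √(2 × 0.30 × 0.70 / 750) = 0.0237, or 2.4 points. The amounts removed are then 1.2 / 2.37 = 0.5 to 3.4 / 2.37 = 1.4 standard errors.

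The result depends almost entirely on the assumed excess. With d = 40%, g = 30% against 10%, and b = 25%, the difference removed is 0.40 × 0.20 × 0.75 = 6.0 points.

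**The case against.** The strongest defence is that the rule is applied equally under blinding and that the signal stays in the report. Grading is unchanged, and Tables 88 and 89 let a reader compare grade 3/4 glucose between arms directly. Deaths and SAEs, the other main safety comparisons, are not redefined. Repeated grade 3 and all grade 4 values in diabetics are kept. This stands, and it limits the harm to the AE counts and the composite. It does not make those counts neutral, because equal application of a rule does not give equal removal when event risks differ by arm.

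A reader might infer more than the document supports:

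- **That the rule removes mainly dexamethasone toxicity.** The SAP gives no rates by arm. Section 4.2.1 also allows one pre-study dexamethasone dose before either assignment, so removed events on baricitinib need not be free of steroid effect.
- **That the rule was driven by the data.** Version 2.0 is written as preceding lock, and Section 4.2.6 has the sponsor and the coordinating center unblinded only after the Day 29 lock. Section 15.2 calls these items clarifications. The SAP does not show whether sites already reported this way, so only the date of the SAP text is known.
- **That a diabetic discharged early cannot meet the two-value rule.** Section 4.3 says "Clinical labs will be drawn on Days 1, 3, 5, 8, 11", but Section 15.2.2 does not limit consecutive values to scheduled draws, and Table 88 uses unscheduled ones. Short stays make a second value less likely, not impossible.
- **That a rise from grade 3 to grade 4 in a non-diabetic has no rule.** Section 15.2 sets the default that grade 3 or 4 results are reported as AEs subject to the clarifications. A case outside the bullets falls under that default. This agrees with Section 9.3, where "treatment emergent events are adverse events or events increasing in severity anytime following the initiation of administration with any study product".

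**Conclusion.** The point holds as a risk of differential event removal, not as a demonstrated bias. The text establishes the unequal treatment of the same grade 3 value by diabetes history, its effect on Tables 61, 76 and 77, and the absence of any planned version without it. The direction is conditional: if dexamethasone carries an excess risk of isolated grade 3 rises in diabetics, the rule lowers its apparent AE burden relative to baricitinib.

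The size cannot be known from the SAP. It is zero with no excess and about 1 to 3 percentage points under the illustrative ranges. Stronger assumptions give more. This justifies a sensitivity analysis and disclosure, not withdrawal of the rule. The primary efficacy analysis is not affected.

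**What to change.** Keep Section 15.2.2 as the AE reporting convention and add two things.

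1. A glucose-only sensitivity version of the grade 3-4 row of Table 61 and of Tables 76 and 77. Any treatment-emergent grade 3 or 4 glucose elevation by DAIDS grade would count, with or without a history of diabetes. Use the Table 89 definition of treatment-emergent (a post-baseline grade above the baseline grade), limited to values through Day 29, and date the event for Table 77 by the first such value.
2. A statement in the report of the reason for the rule, and of when it was introduced into the SAP and at sites. The two dates may differ.

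The analysis should stay with glucose. Extending it to all laboratory parameters would turn an AE endpoint into a laboratory endpoint. It would also run into INR, which Section 15.2.3 deliberately leaves ungraded in subjects on anticoagulants.

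The cost is one extra row and two extra tables from values already graded for Tables 88 and 89. The downside is that some transient rises that clinicians may consider expected would be counted, so the result should be labeled as a sensitivity analysis beside the planned tables.
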